### 7.2.3 Safety assessments

Unless otherwise specified, the date of each assessment will be collected in the eCRF.

The definitions, reporting, and follow-up of AEs, SAEs, and pregnancies are described in Section 8.

#### 7.2.3.1 *Physical examination*

A full and complete physical examination will be performed at Visits 1, 2, 3, 5, 8, 11, 14, and 15. Full and complete physical examination includes the examination of the following body parts/systems:

- Head, ear, nose, mouth, and throat
- Eyes
- Neck
- Cardiovascular system
- Respiratory system
- Abdomen
- Skin
- Extremities
- Neurological system
- Musculoskeletal system

Other exams will be performed if indicated, based on medical history and/or symptoms.

For all other visits, a symptom-driven abbreviated physical examination will be performed to capture assessments needed for the SLEDAI-2K, the PGA, the BILAG, and the SFI.

For details on skin examination, please refer to Section 7.2.3.9.

Information for all physical examinations must be included in the source documentation at the study site.

All findings, including clinically not relevant findings that are present prior to signing the ICF, must be recorded as medical history or SLE-relevant disease history in the eCRF.

Physical examination findings after signing the ICF which meet the definition of an AE [Section 8.1.1] must be recorded as an AE in the eCRF.

### **7.2.3.2 Weight and height**

Height will be measured and recorded in the eCRF at Visit 1 (Screening). Participant body weight will be measured (heavy clothing should be removed) and recorded in the eCRF at Visit 1 (Screening), Visit 14 (EOT), and Visit 20 (FSV). For further body weight measurements as part of the BILAG assessment at each applicable visit [see Section 7.2.2.2], the weights will be recorded in the source documentation and if clinically relevant, the body weight collected outside Visit 1 (Screening), Visit 14 (EOT) and Visit 20 (FSV) may be reported as an unscheduled assessment in the eCRF.

### **7.2.3.3 Electrocardiograms**

#### *7.2.3.3.1 Cardiac monitoring applicable to all participants*

ECGs will be performed at pre-dose for all participants at all scheduled visits with the participant in a fully rested supine position after the participant has been allowed to rest for a minimum of 5 minutes prior to the measurement. Single digital 12-lead ECG will be performed using the ECG machine provided by the central ECG vendor. The date and actual time of ECGs will be recorded in the eCRF.

A central ECG vendor (see ECG manual for contact details) will be used for the evaluation of all protocol-mandated ECGs, including re-tests due to ECG abnormalities and ECGs performed at unscheduled visits. The site personnel will electronically transmit the ECGs to the central ECG vendor for central reading as soon as possible after the examinations.

The 12-lead ECG measurements will evaluate the following variables: HR (bpm), PR (ms), QRS (ms), QT (ms), QTc (ms), and any ECG findings. The QTc (ms) will be calculated according to Bazett's and Fridericia's formula ( $QTcB = QT/(RR)^{1/2}$  and  $QTcF = QT/(RR)^{1/3}$ , respectively). The ECG findings (e.g., rhythm, ectopy, conduction, and morphology) and the overall interpretation of the ECG (normal/abnormal) will be provided by the ECG central vendor to the study site and to sponsor.

At Visit 2 Day 1, the pre-dose ECG must be performed for all participants and interpreted by the investigator/delegate prior to study drug administration. The applicable cardiac exclusion criteria 7, 8, 9 and 10 must be ruled out.

In addition to transmitting the ECG to the central reader, an ECG record at the Visit 2 must be printed, signed, and dated by the person interpreting the ECG and determining that the relevant exclusion criteria were not met.

ECG reports will be provided by the central ECG vendor to the investigator/delegate. If specific (pre-defined in the ECG manual) ECG abnormalities are observed, the central ECG vendor will alert the sponsor and the investigator/delegate.

All ECG reports obtained from the central ECG vendor must be reviewed, signed, and dated by the investigator/delegate within 10 calendar days of receipt and filed with the source documentation. The investigator/delegate must indicate on the ECG report whether abnormal values or findings are considered clinically relevant or not. All ECG findings, including clinically not relevant findings, that are present at the time of signing the ICF must be recorded on the medical history page in the eCRF. Any clinically relevant ECG abnormalities detected after signing the ICF must be reported as an AE or SAE as appropriate [see Section 8.2] and must be followed until the finding returns to normal, is considered stable, or until the change is no longer clinically relevant. Notable abnormalities are detailed in Appendix 13 and marked abnormalities will be detailed in the SAP.

Details on ECG procedures (recording, transfer of data and reporting) will be provided in the ECG manual.

#### *7.2.3.3.2 Additional cardiac monitoring on Day 1*

To evaluate the possible transient effects on BP and HR after study treatment initiation with S1P receptor modulators, 12-lead ECGs and BP assessments will be additionally performed as post-dose cardiac monitoring for all participants on Day 1 and at study treatment re-initiation visit(s).

The post-dose cardiac monitoring will consist of post-dose 12-lead ECGs, performed hourly within 12 hours post dose, and BP assessments, performed hourly within 6 hours post dose and at 12 hours post dose as per the SoA. At 12 hours the participant may be discharged from monitored setting if they meet the discharge criteria [see Appendix 5] If the participant does not meet the discharge criteria at 12 h post-dose, the participant will be permanently discontinued from the study treatment and will be kept in the monitored setting for observation.

Any cardiac events of potential clinical concern on Day 1 and on the first day of re-initiation visit must be assessed by the investigator or their delegate for seriousness. In addition, the investigator or their delegate should determine the need for medical management and decide what actions should be taken on study treatment, if any. The investigator or their delegate may consult with a cardiologist. In cases of acute cardiac events, and if they are not adequately trained and experienced in cardiology and are not equipped to provide emergency treatment, she/he will refer the participant to a cardiologist to receive emergency care and treatment.

#### 7.2.3.4 Clinical laboratory assessments

See Appendix 1 for the list of clinical laboratory tests to be performed. See the SoA [Table 1, Table 2, and Table 3] for the timing and frequency.

At unscheduled visits, blood samples will be collected at the investigator's discretion. Sample collection dates will be recorded in the eCRF [for biomarkers see Section 7.2.6].

Blood samples will be drawn in the morning under fasted conditions (i.e., before breakfast) and when applicable before the morning administration of the study treatment at all scheduled and unscheduled visits. However, it is not permitted to request that participants are in a fasted state (for the study) at Screening unless the ICF has already been fully signed.

A midstream, clean-catch urine specimen will be collected according to the SoA [Table 1, Table 2, and Table 3] and sent to the central laboratory for analysis using urine dipsticks. If the dipstick results are positive for protein, leukocytes, or blood, the urine sample will be subject to further analysis (i.e., microscopic analysis). The results will be used for assessment of the mSLEDAI-2K and BILAG scores.

Urine protein-to-creatinine ratio is to be determined using urine samples sent to the central laboratory for analysis of protein and creatinine. For the assessment of proteinuria, the protein-to-creatinine ratio in a single urine sample has been demonstrated as strongly correlated with the protein content of a 24-hour urine collection [Ginsberg 1983, KDIGO 2012, Price 2005, Ruggenenti 1998]. For this reason, the result from urine protein-to-creatinine ratio can be used in this study for assessment of both the mSLEDAI-2K and BILAG scores. The relationship among these laboratory tests for proteinuria is provided below in Table 7 [KDIGO 2012]. If the results of the protein-to-creatinine ratio are below the lower limit of quantification, this must be recorded as "not determined" in the questionnaires and justification has to be provided.

**Table 7 Relationship among laboratory tests for proteinuria**

Measure	Unit	Conversion factor
24-hour urine protein excretion rate	g/24 hours	1
	mg/24 hours	1000
Urine protein-to-creatinine ratio	mg/g	1000
	mg/mmol	100*

\* The conversion is rounded for pragmatic reasons. For an exact conversion from mg/g of creatinine to mg/mmol of creatinine, multiply by 0.113.

A serum pregnancy test for WoCBP will be performed at Screening (Visit 1) and a urine pregnancy test prior to study drug administration Visit 2. Both must be negative and performed at least 3 weeks apart. A second serum pregnancy test is performed at Visit 20 (FSV). Serum pregnancy tests will be sent to the central laboratory for analysis and the result will be sent to the investigator/delegate.

Urine pregnancy tests will be performed at all other visits with kits provided by the central laboratory. Urine pregnancy kits will be provided to WoCBP at follow-up Visit 15 for use by the participant during the follow-up phone call Visits 16, 17, 18, 19, and the results collected during the scheduled phone calls. The results of the urine pregnancy tests, including those performed at home by the participants, will be collected in the eCRF. If pregnancy is suspected during the study, i.e., in each case of delayed menstrual period (e.g., over 1 month between menstruations), positive urine pregnancy test, etc., a serum pregnancy test must be performed as soon as possible. Reporting procedures of pregnancy are described in Section 8.3.1.

A central laboratory (see central laboratory manual for contact details) will be used for all protocol-mandated laboratory tests, including retests due to laboratory abnormalities and laboratory tests performed at unscheduled visits.

Exceptional circumstances that may require recording of local laboratory results of the variables described in Appendix 1 include hospitalization of the participant due to a medical emergency, inability to travel to the study site due to reasonable reasons judged by investigators and missing central laboratory results from a scheduled or unscheduled visit. The local laboratory results (with the corresponding normal ranges) must be recorded in the eCRF.

If central laboratory samples are lost or cannot be analyzed for whatever reason, the investigator/delegate will collect an additional sample as soon as possible for repeat analysis, unless a local laboratory sample was collected within the same time frame and these test results are available.

Central laboratory reports will be sent to the investigator/delegate. In the event of specific (pre-defined) laboratory abnormalities, the central laboratory will alert the sponsor personnel and the concerned site personnel. Alert flags that trigger such notifications will be displayed in the laboratory manual.

All laboratory reports must be reviewed, signed and dated by the investigator/delegate within 10 calendar days of receipt and filed with the hospital chart. The investigator/delegate must indicate on the laboratory report whether abnormal values are considered clinically relevant or not. Laboratory findings that are present at the time of signing the ICF must be recorded on the Medical History page in the eCRF. Any clinically

relevant laboratory abnormalities detected after signing the ICF must be reported as an AE or SAE as appropriate [see Section 8] and must be followed until the value returns to within the normal range or is stable, or until the change is no longer clinically relevant. Notable abnormalities are detailed in Appendix 13.

Details about the collection, sampling, storage, shipment procedures, and reporting of results and abnormal findings can be found in the laboratory manual.

#### ***7.2.3.5 Ophthalmological examination***

The purpose of the ophthalmology assessment prior to cenerimod treatment is to document a baseline assessment as well as to exclude participants with macular edema, retinal vasculitis, or active uveitis from the study. Assessments at other visits will ensure that any new ophthalmological abnormality is detected and treated at an early stage.

An ophthalmological examination will be performed by an ophthalmologist at any time during the screening period, but results must be available prior to Visit 2. Examinations after Screening will be performed as per schedule of assessments [see Table 2].

The ophthalmological examination should include previous eye history and ophthalmic conditions, any new or current ophthalmological symptoms, assessment of best corrected visual acuity per local standard practice, measurement of ocular pressure by the Goldmann applanation tonometry (recommended, if not available other tonometer allowed; in case the assessment is performed by rebound tonometry and result is abnormal, confirmation by applanation tonometer must be performed), slit lamp examination of the anterior segment, and fundoscopy. While the visual acuity and applanation tonometry exams may be performed by a delegate (e.g., experienced technician, optometrist), the review and interpretation must be performed by an ophthalmologist. Conduct, review, and interpretation of all other ophthalmological exams must be performed by an ophthalmologist.

In the eCRF, the date of the ophthalmological examination and the presence/absence of any abnormality and clinical assessment results (i.e., Normal, NCS abnormal and CS abnormal) will be recorded. Clinically relevant findings that are present at the time of signature of the ICF must be recorded on the medical history page of the eCRF. Any clinically relevant ophthalmological abnormalities (including OCT findings) detected after signature of the ICF must be reported as an AE or SAE as appropriate [see Section 8.1.1] and must be followed until the value returns to within the normal range or is steadily improving.

For participants with suspected macular edema or retinal vasculitis, the diagnosis should be confirmed by diagnostic work-up as recommended by local guidelines (e.g., OCT or fluorescence angiography).

#### **7.2.3.6 *Optical coherence tomography***

OCT will be performed at as per the SoA. Testing at Visit 1 can be performed at any time during the screening period. At all other visits, testing may be performed up to 7 days prior to the visit date but no later than 7 days after the visit.

In addition, unscheduled OCT examination must be performed in the event of visual symptoms or findings suggestive of macular edema according to the ophthalmologist's decision or if active uveitis is diagnosed during the study. While the OCT exam may be performed by a delegate (e.g., experienced technician, optometrist), the review and interpretation must be performed by an ophthalmologist.

The purpose of the assessment prior to Visit 2 is to exclude participants with macular edema or active uveitis from the study, and to document a baseline assessment. The site will use the OCT device available locally and must ensure it is working properly. A copy of the calibration certificate or evidence of equipment maintenance performed prior to the assessment must be stored as source documents at the site. To the extent that is logistically feasible, the same OCT machine is recommended to be used for each individual participant throughout the study.

In the eCRF, the date of the OCT assessment and the presence/absence of any abnormality and clinical assessment results (i.e., Normal, NCS abnormal and CS abnormal) will be recorded. Any clinically relevant abnormalities detected after signature of the ICF must be reported as an AE or SAE as appropriate [see Section 8.1.1].

#### **7.2.3.7 *Chest X-ray or CT scan***

A chest X-ray or CT scan will be performed at Visit 1 (Screening) and assessed by the local radiologist to support the assessment of eligibility criteria (e.g., exclude any participant with active or latent TB). Chest X-ray or CT scan testing can be performed at any time during the screening period. If results of a chest X-ray or CT scan that has been performed within 6 months prior to Screening do not demonstrate active or latent TB, there is no need to repeat the chest X-ray or CT scan at Screening. The report of the chest X-ray or CT scan must be recorded in the participant's file.

#### **7.2.3.8 *Test for tuberculosis***

An IGRA will be performed at Visit 1 (Screening) to screen for active or latent TB, unless one of the exceptions as detailed in the exclusion criterion have been met. The test will be analyzed and interpreted at the central laboratory and transferred to the investigator.

Details on the performance of the test for TB will be provided in the specific central laboratory manual.

### **7.2.3.9 Skin examination**

Each physical examination must include a complete skin examination performed by the investigator/delegate. In the event of findings other than skin findings relevant to SLE, a dermatologist will conduct further examination per local standard practice, including performing skin biopsies if required to rule out or confirm a diagnosis.

### **7.2.4 Blood pressure assessments**

The investigator/delegate is responsible for BP measurements, including SBP and DBP. BP will be assessed as per the SoA.

For a given participant, BP measurements will be performed using the same type of device throughout the study on the same arm with the participant in a fully rested supine position after the participant has been allowed to rest for a minimum of 5 minutes prior to the measurement. At all visits (including Visit 1/Screening visit), SBP and DBP will be measured twice. The SBP/DBP assessment will be performed pre-dose at all visits during the study treatment period. Each of the 2 obtained measurements (i.e., 2 SBP measurements and 2 DBP measurements) and the position and arm used are to be recorded in the eCRF. The means of the 2 obtained measurements will be calculated in the eCRF. Any clinically relevant BP abnormalities detected after informed consent signature must be reported as an AE or SAE as appropriate [see Section 8.2].

At Visit 2 (Day 1) and at study treatment re-initiation, the post-dose SBP/DBP assessments will be performed in parallel to 12-lead ECGs.

The post-dose SBP/DBP assessments will only be measured once at each hourly time point until 6 h post-dose and at hour 12 post-dose. At the 12-hour post-dose timepoint, participants may be discharged from the monitored setting if they meet the pre-specified discharge criteria [see Appendix 5]. Refer to Appendix 5 regarding participant discontinuation and monitoring if discharge criteria not met.

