 The post dose 12-lead ECGs assessments will be measured once at each hourly time point within 12 hours post-dose, while SBP/DBP assessments will be measured once at each hourly time point within 6 hours post-dose and at 12 hours post-dose at Visit 2 (Day 1) and at study treatment re-initiation. At the 12-hour post-dose timepoint, participants may be discharged from the monitored setting if they meet the pre-specified discharge criteria. For discharge criteria see Appendix 5.

 Physical examination will only be performed at Visits 1, 2, 3, 5, 8, 11, 14, and 15. For all other visits, a symptom-driven abbreviated physical examination will be performed to capture assessments needed for the SLEDAI-2K, the PGA, the BILAG, the CLASI and the SFI.

 Body weight (measured under fasting conditions in the morning) should be recorded in the BILAG assessment page in the paper sheets at all visits in which this assessment is performed. It should also be recorded in the eCRF at Visits 1, 14, and 20.

 At all visits, a single pre-dose 12-lead ECG will be performed and transmitted to the central reader. A pre-dose SBP/DBP will be performed at all visits (including Screening) in duplicate and both values, including the arm and position used, will be entered into the eCRF.

 Aldolase to be measured only at investigator's request.

 A central laboratory will be used for all protocol-mandated laboratory tests, including retests due to laboratory abnormalities and laboratory tests performed at unscheduled visits. Local laboratory tests may be required under exceptional circumstances and results should be recorded as unscheduled local laboratory in eCRF.

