#### *5.8.1.4.1 Day 1 specific stopping criteria*

Cardiac monitoring on the first dose on Day 1 and on the first day of re-initiation of study treatment will be required for participants.

Participants **must** be permanently discontinued from study treatment if any of the following occurred on Day 1 or on the day of re-initiation:

- HR < 40 bpm at two consecutive hourly 12-lead ECG post-dose assessments;
- SBP < 90 mmHg at two consecutive hourly BP measurements post-dose;
- For participants with baseline pre-dose SBP < 90 mmHg: decrease in SBP of > 5 mmHg from pre-dose SBP value at two consecutive hourly BP measurements post-dose;
- The participant does not meet the criteria for discharge from the monitored setting at 12-hour post-dose.

Close monitoring (ECG or BP, as appropriate) is recommended for participants who meet study treatment discontinuation criteria as detailed in Appendix 5.

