#### *5.8.1.4.2 Other cardiovascular stopping criteria*

- If participant presents with a QTcF of > 500 ms (females) or > 480 ms (males) at any time throughout the study, as measured and documented by 12-lead ECG, a re-test should be performed at the same visit. If at re-test, QTcF is confirmed > 500 ms (females) or > 480 ms (males), the participant must be permanently discontinued from study treatment. Participants with QTcF prolongation should be monitored until the absence of the persisting ECG abnormality can be confirmed.
- Symptomatic bradycardia or hypotension (e.g., syncope) at any time.

If any of those criteria are met, it will be recorded as an AE/SAE, and follow-up monitoring will have to be provided until the AE resolves and the participant's condition is stable.

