## **Appendix 5 Criteria for discharge from monitored setting on Day 1 and on the first day of re-initiation following treatment interruptions**

At the 12 hours post-dose on Day 1 and on the first day of re-initiation of study treatment following treatment interruptions lasting for at least 7 days in the first 14 days of treatment, all the following criteria must be met:

- ECG-derived resting HR > 45 bpm; *and* if HR < 50 bpm it must not be the lowest value measured post-dose;
- SBP  $\geq$  90 mmHg;
- For participants with baseline pre-dose SBP < 90 mmHg: decrease in SBP of  $\leq$  5 mmHg from pre-dose SBP value;
- QTcF < 500 ms (females) or < 480 ms (males);
- No newly occurred persistent clinically significant ECG abnormality (e.g., AV block second-degree or higher) or ongoing AE requiring continued hospitalization;
- No other clinically significant symptoms, signs or abnormalities as per judgment of the investigator.

If at 12 h post-dose the participant does not meet discharge criteria, he/she must be permanently discontinued from study treatment. Participants who are permanently discontinued should not be discharged from the monitored setting before the HR abnormalities and BP return to near baseline values and until there are no persistent ECG abnormalities (e.g., AV block second-degree or higher) or ongoing AE requiring continued hospitalization, or until a diagnosis is established.

Discharge criteria will be recorded in the eCRF.

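### A first low SBP at 6 h after the Day 1 or re-initiation dose has no scheduled confirmatory reading, so the two-consecutive-hourly stopping rule cannot be completed from it

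*Combined protocol and SAP*

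**What the plan says.** Section 5.8.1.4.1 applies on Day 1 and on the day of any re-initiation. It makes permanent discontinuation mandatory for "SBP < 90 mmHg at two consecutive hourly BP measurements post-dose". For participants whose pre-dose SBP is below 90 mmHg, the trigger is instead a fall of more than 5 mmHg, again at two consecutive hourly readings.

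Three places set the post-dose BP schedule, and they agree:
- Table 2, footnote 1: "SBP/DBP assessments will be measured once at each hourly time point within 6 hours post-dose and at 12 hours post-dose".
- Section 7.2.3.3.2: "BP assessments, performed hourly within 6 hours post dose and at 12 hours post dose as per the SoA".
- Section 7.2.4: "The post-dose SBP/DBP assessments will only be measured once at each hourly time point until 6 h post-dose and at hour 12 post-dose".

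The 12-lead ECGs that serve the matching heart-rate rule are hourly all the way to 12 h.

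Other provisions bear on low BP that day. Appendix 5 includes SBP among the 12 h discharge criteria and adds: "If at 12 h post-dose the participant does not meet discharge criteria, he/she must be permanently discontinued from study treatment". Section 5.8.1.4.2 lists "Symptomatic bradycardia or hypotension (e.g., syncope) at any time" as a stopping criterion.

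**The concern.** The rule needs two readings one hour apart, but the schedule stops supplying such pairs after 6 h. Low SBP at 5 h and 6 h forces a permanent stop. The same values at 6 h and 7 h force nothing under the plan as written: the second is not scheduled, and if SBP has recovered by 12 h the participant can be discharged and continue daily dosing.

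The scheduled recheck also disappears near the expected first-dose peak. Section 2.2 gives a median tmax of 5–6 h after a single dose in healthy participants, and Section 2.4.2 puts the maximum heart-rate decrease at 6 h. This is PK and heart-rate evidence, not BP evidence, but it is where one would least want the confirmatory reading to be missing.

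A site may take an extra reading at 7 h. Nothing requires it, and nothing says how it enters the rule, so identical 6 h values could be handled differently across the planned 5–10 sites.

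**Working it through.** The plan states no figure to reproduce here. The check is a count of scheduled time points, followed by an illustration that rests on an assumed incidence.

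**Scheduled times.** BP (Table 2 footnote 1, Sections 7.2.3.3.2 and 7.2.4): 1, 2, 3, 4, 5, 6 and 12 h. ECG (Table 2 footnote 1, Section 7.2.3.3.2): 1, 2, …, 12 h.

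**Pairs exactly one hour apart.**

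| Series | Readings | Hourly pairs | Last pair |
|---|---|---|---|
| BP | 7 | 5 | 5–6 h |
| ECG (heart rate) | 12 | 11 | 11–12 h |

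**Wait after a first low SBP.** At 1, 2, 3, 4 or 5 h the next scheduled reading is 1 h later. At 6 h it is 12 − 6 = 6 h later. This holds even if the rule is read as covering only the 1–6 h series, because the 6 h value belongs to that series and ends it. Treating 6 h and 12 h as a pair does not fit the word hourly in the rule.

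**Episodes that escape both numeric checks.** Take a continuous low-SBP episode covering at least two whole hours between 1 h and 12 h. It is caught if it includes a scheduled hourly pair, or if it is still present at 12 h. Those not caught are:
- onset 6 h, last low hour 7, 8, 9, 10 or 11: 5 patterns
- onset 7 h: 4 patterns; 8 h: 3; 9 h: 2; 10 h: 1

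The total is 5 + 4 + 3 + 2 + 1 = 15 patterns. In the five that start at 6 h, the plan sees the low value and schedules no follow-up. In the other ten, no scheduled reading falls inside the episode. These are patterns, not probabilities.

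**Illustrative frequency.** Let p be the chance that a participant has a first qualifying low at 6 h on Day 1. The documents give no value, so p is an assumption, with participants taken as independent. With 15 participants (Section 9.4), P(at least one) = 1 − (1 − p)^15 and the expected number is 15p.

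| Assumed p | P(at least one of 15) | Expected number |
|---|---|---|
| 1% | 1 − 0.99^15 = 14% | 0.15 |
| 2% | 1 − 0.98^15 = 26% | 0.30 |
| 5% | 1 − 0.95^15 = 54% | 0.75 |
| 10% | 1 − 0.90^15 = 79% | 1.5 |

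These are the chances that the situation arises, not that a stop is missed. Some participants would recover by 7 h and need no stop. Others would still be low at 12 h, have symptoms, or be stopped on judgment. The probability of a missed stop is lower than each figure by an amount the documents do not allow one to estimate.

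**The case against.** The strongest reply is that other provisions already cover most of this, and much of that reply stands.

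- **12 h gate.** One failing SBP at 12 h ends treatment, which is stricter than the two-reading rule. Any episode lasting to 12 h is caught.
- **Symptoms.** Symptomatic hypotension is a stopping criterion whenever it occurs.
- **Judgment.** Section 7.2.3.3.2 says: "Any cardiac events of potential clinical concern on Day 1 and on the first day of re-initiation visit must be assessed by the investigator". Discharge also requires: "No other clinically significant symptoms, signs or abnormalities as per judgment of the investigator". Section 5.8.1.4 has clinically relevant vital-sign abnormalities recorded as AEs, and Section 5.8.1.1 obliges the investigator to stop when continuing is against the participant's interests.
- **Extra readings.** The rule is not worded as limited to scheduled readings, and unscheduled assessments are allowed, so a 7 h repeat could count.
- **Risk.** Section 2.4.4 reports no consistent or dose-dependent BP change over time in the Phase 2b study. Hourly BP through the quoted tmax and heart-rate nadir, followed by a strict 12 h gate, is a defensible design.

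What these points do not supply is a requirement to repeat the reading. The sponsor chose a mandatory numeric rule, while the remaining safeguards depend on symptoms or discretion. The close-monitoring recommendation in Section 5.8.1.4.1 does not help either: it applies to participants who already meet a discontinuation criterion, and a single low at 6 h does not.

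**Conclusion.** The concern holds. The SBP stopping rule and the BP schedule do not fit together at 6 h, the only reading in the 1–6 h series without a scheduled reading one hour later. The matching heart-rate rule has no such break at 6 h.

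The consequence is small. What goes unaddressed is asymptomatic low SBP that starts at 6 h or later, resolves by 12 h and is not acted on by judgment. Expected risk is low given the Phase 2b BP findings. The 14% to 79% range rests wholly on assumed rates of 1% to 10% and should not be read as a rate of missed stops. No sample size or error rate is affected. Confidence is high on the mismatch itself; its frequency is unknown. This is an inexpensive improvement the sponsor could make, not a flaw that undermines the study.

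**What to change.** In Table 2 footnote 1 and Sections 7.2.3.3.2 and 7.2.4, add: if SBP at 6 h meets a threshold in Section 5.8.1.4.1, repeat BP at 7 h and then hourly until it no longer does; the 6 h and 7 h readings count as two consecutive hourly measurements for the stopping rule. The 7 h reading settles the rule; later ones are for monitoring.

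**Cost.** One extra reading settles each case, so 0 to 15 × 1 = 15 such readings on Day 1, and one more at any re-initiation visit with a first low at 6 h. If SBP stays low to 11 h, the maximum is 5 per participant (7, 8, 9, 10 and 11 h). The participant is already in the monitored setting with an ECG due at 7 h. The downside is possibly an occasional additional discontinuation.

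**Optional fuller change.** The triggered repeat closes only the five patterns that start at 6 h. Measuring BP hourly to 12 h alongside the ECGs would raise the hourly pairs from 5 to 11 and also cover onset at 7–10 h. It adds 5 readings per participant, or 15 × 5 = 75 on Day 1, plus 5 per re-initiation visit.
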